4.3 PATIENT RECRUITMENT

4.3.1 Recruitment strategies

4.3.1.1 Research sites

Based on the clinical audit of children attending paediatric gastroenterology clinics, Alder Hey Hospital during 1 month [5], 40 children fulfilled Rome IV criteria [21] for a FAPD (Group H2). A more recent audit at both sites of children attending general paediatric and paediatric gastroenterology clinics estimated each site could recruit 5-10 patients from a potential 20-40 eligible patients.

With the inclusion of patients previously diagnosed with an FAPD and considering difficulties in recruitment to clinical trials especially of older children, recruiting a total of 13 patients per month for 12 months is a realistic target.

Recruitment will be competitive across all sites until the total target of 154 patients has been met. All participating sites will be required to participate in a site initiation and training meeting and regular followup meeting to track progress organised by the study Sponsor.

An additional recruitment option will be considered if recruitment rates are slower than estimated. Research nurses will screen for children previously diagnosed with an FAPD and send out an invitation to join the study and include the patient information sheets.

4.3.2 Screening process

Potentially eligible patients will be identified by review of NHS referrals to general paediatric and paediatric gastroenterology clinics at Alder Hey Children's NHS Foundation Trust, and Bristol Royal Hospital for Children and also by review of children previously diagnosed with a FAPD. All children will be reviewed by an experienced paediatrician.

The diagnosis of a FAPD and the sub-type will be confirmed by a study paediatrician after undertaking appropriate clinical investigations if required. Participants deemed eligible to join the study and/or their parents/carers will be provided with verbal information regarding the trial and an age-appropriate Patient Information Sheet by the study paediatrician or in the post for previous diagnosed patients. If they are interested in considering joining the trial a pregnancy kit (if required) will be provided for the subject to use, after securing informed consent. They will then be contacted by the Research Nurse after they have had 24 hours to consider the study, to arrange the remote Recruitment appointment. At the remote Recruitment appointment, eligibility will be confirmed, and e-consent and assent will be obtained by the research nurse before any study procedures are conducted. Medical history and list of concomitant medications will be obtained from the screening form and/or medical notes. Information and a demonstration on the e-diary, questionnaires and study treatment will be provided.

Basic information about all screened patients will be documented in a study screening log and/or eCRF at the research site (age, sex, ethnicity). The patient's GP will be notified of the patient's participation in the study and will maintain the responsibility for the healthcare of the patient outside the research.

A patient must not be randomised at Baseline before the results from any tests required to exclude other conditions and a negative pregnancy test, if applicable, have been obtained. Eligibility must be confirmed against the patient's medical notes as stated in section 4.2.

4.4 DISCONTINUATION AND WITHDRAWAL CRITERIA

Participants or parents/carers can withdraw consent at any time without providing a reason. This includes during the initial 2-week observation phase and before receiving any interventions. No further data will be collected after a participant withdraws consent or is withdrawn from the study, but data collected before withdrawal can be used. If a participant refuses to continue the use of study treatment, they can continue with follow-up assessments and visits if willing to do so, but a Protocol Deviation for non-compliance to study treatment should be recorded.

In case of the following the participants should be withdrawn from the study by the Principal Investigator:

- Significant deterioration of the participant's status as assessed by the principal investigator
- Serious Adverse Event (SAE) related to study treatment(s) or procedures
- Pregnancy

- Any other changes in diagnoses or medical conditions that could affect participants safety on the trial and/or scientific quality of the data
- Major protocol violation (affecting participants safety and/or scientific quality of the data)

The reason(s) for withdrawal should be documented in the Continuation Status eCRF as soon as site becomes aware of the patient's withdrawal. If a participant decides to withdraw consent or is lost to followup, this should also be documented in the Continuation Status eCRF without delay. Participants should be informed that they might be contacted in the future if any significant new information becomes available regarding the study treatment.

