8.2.4 Handling of missing data

Where appropriate, multiple imputation will be used to impute missing values under a missing at random assumption in order to avoid excluding patients from the analysis. Multiple imputation involves creating multiple copies of the data set, with the missing values replaced by imputed values drawn from their predicted distribution by using the observed data [24].

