8.3 ANALYSIS POPULATIONS

8.3.1 Intention-to-treat population (ITT)

ITT population will include all randomised patients analysed in the groups to which they were randomised to, regardless of whether they received or adhered to the allocated intervention.

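### Children withdrawn by the investigator also leave data collection, so the follow-up that an ITT comparison needs is lost for reasons that can depend on outcome or treatment

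*Protocol*

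**What the plan says.** Section 4.4 states: "No further data will be collected after a participant withdraws consent or is withdrawn from the study". The same sentence allows data gathered earlier to be used. The section then lists grounds on which "the participants should be withdrawn from the study by the Principal Investigator". The first is "Significant deterioration of the participant's status as assessed by the principal investigator". The others are an SAE related to study treatment or procedures, pregnancy, other changes in diagnosis or condition bearing on safety or data quality, and a major protocol violation. Section 5.3.1 adds withdrawal from the trial for a child who comes to need slow-release medication.

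Other cases are handled differently. Under 4.4, a child who refuses further treatment may stay in follow-up, with a deviation recorded. Under 6.4, an unblinded child is followed to the end of the study even though the investigator may stop treatment.

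Section 8.2 makes the primary analysis intention-to-treat. Section 8.3.1 includes all randomised children "regardless of whether they received or adhered to the allocated intervention". For gaps, section 8.2.4 says that, where appropriate, "multiple imputation will be used to impute missing values under a missing at random assumption".

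**The concern.** Deterioration can be the outcome itself, and a related SAE is by definition tied to treatment. Ending data collection at those moments removes the observations that show how such children fared under the arm they were assigned to. An analysis plan can add sensitivity analyses, but it cannot recover diary entries that were never requested.

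Ending data collection for a major violation also fits badly with a comparison meant to hold regardless of adherence. Section 10.2 lists repeated non-compliance and taking no study treatment among its examples of violations. A child who stops treatment could therefore be read as free to stay in follow-up (4.4, refusal) or as liable to be withdrawn (4.4, major violation).

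At stake are the primary treatment difference and, for withdrawn children, non-serious adverse events and the week 6 and week 10 questionnaires.

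**Working it through.** **1. The passages side by side**
- 4.4 against 8.3.1: withdrawn children remain in the ITT set and their earlier data count. Their later outcomes are missing by rule, not by the family's choice.
- 4.4 against 7.2.1 and 7.3: 4.4 ends all data collection. Section 7.2.1 follows SAEs to resolution or final outcome, and 7.3 withdraws a pregnant participant yet follows the pregnancy to outcome. These cannot all be applied literally.
- 4.4 against 6.4: unblinded children are kept in follow-up; children withdrawn by the investigator are not.

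**2. Upper-range arithmetic**

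The plan gives no figure for investigator withdrawals, so there is none to reproduce. Section 8.1 gives the planned mean changes (-2.2 on Enterosgel, -1.2 on placebo, a difference of 1.0) and a 15% drop-out allowance not split by reason. Assumptions: shares withdrawn pE and pP; a true mean change t of 0 to +2 in withdrawn children; no usable post-baseline diary; imputation at the planned mean of the child's own arm.

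Bias in the difference (Enterosgel minus placebo) = pE × (-2.2 - t) - pP × (-1.2 - t). Negative values favour Enterosgel.

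- pE = 0.08, pP = 0.03, t = 0: -0.176 + 0.036 = -0.14
- pE = 0.08, pP = 0.03, t = 2: -0.336 + 0.096 = -0.24
- pE = 0.03, pP = 0.08, t = 0: -0.066 + 0.096 = +0.03
- pE = 0.03, pP = 0.08, t = 2: -0.126 + 0.256 = +0.13

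Of 77 children per arm, 8% is about 6 and 3% about 2. The formula has a built-in tilt: with equal shares of 5% it still gives 0.05 × (-2.2 + 1.2) = -0.05, because it imputes different arm means but assumes one common true change.

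**3. A form without that tilt**

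Let k be how much worse the true four-week mean of withdrawn children is than the imputed one, the same in both arms. The apparent benefit is then inflated by k × (pE - pP). With shares of 0 to 15% and k of 1 to 3, this runs from 0 at equal shares to 3 × 0.15 = 0.45 points in either direction.

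**4. When missing at random holds**

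A simulation used weekly diary means over weeks 3-6, a planned difference of -1.00, assumed variances, loss of weeks 5-6 after withdrawal, and regression imputation within arm from children who stayed.
- Withdrawal triggered by a worse week-4 score already recorded (about 10% placebo, 3% Enterosgel): imputed difference -1.00 against a true -1.00; completers alone give -0.87.
- A 2-point worsening only after the last entry:
  - 10% placebo, 5% Enterosgel: true -1.05, imputed -1.00
  - 5% placebo, 10% Enterosgel: true -0.95, imputed -1.00
  - 15% placebo, 0% Enterosgel: true -1.15, imputed -1.00
  - 0% placebo, 15% Enterosgel: true -0.85, imputed -1.00

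The second set agrees with step 3: 2 points over 2 of 4 weeks gives k = 1, and 1 × 0.05 = 0.05 or 1 × 0.15 = 0.15.

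**The case against.** The strongest defence is that missing at random is conditional on what was observed. Pain is recorded daily from week 1, so a child withdrawn for worsening pain will often have that worsening in the diary, and imputation can then be unbiased, as step 4 shows. This stands. A reader might infer that the rule makes the imputation wrong; the documents do not support that. What remains is that the assumption fails if the worsening follows the last entry, and the rule ensures that nobody can check. Imputing from children who stayed also estimates outcomes as if treatment had continued, which is not the comparison regardless of adherence.

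A reader might also infer that 4.4 contradicts the ITT definition. It does not: 8.3.1 defines a set, withdrawn children remain in it, and 4.4 keeps their earlier data. The tension is with the full follow-up that an ITT comparison needs.

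Other points also stand:
- The deterioration criterion refers to the child's status, not specifically to pain. Pregnancy, changed diagnosis and violations are not clearly outcome-dependent, and only major violations lead to withdrawal.
- Refusers are not the only children kept in follow-up after stopping treatment; section 6.4 keeps unblinded children too.
- The safety record is not simply cut short. SAE and pregnancy follow-up is required elsewhere, so for those the problem is contradiction; the plausible loss is non-serious events.
- Sensitivity analyses may be in the SAP, which is not shown. Their absence here is no finding.

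**Conclusion.** The point holds in this form: section 4.4 discards obtainable follow-up for reasons that can depend on outcome or treatment, leaves the missing-at-random assumption doubtful and untestable for these children, and conflicts with 7.2.1 and 7.3. I would class it as should-fix.

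The size is not known. The 0.14 to 0.24 points towards Enterosgel, and 0.03 to 0.13 the other way, rest on assumed rates and on ignoring partial diaries. If half the treatment window is recorded and only the rest is imputed in this way, they halve to 0.07-0.12 and about 0.02-0.07. Withdrawals after week 6 do not affect the primary endpoint.

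A reader might infer a bias in favour of Enterosgel. The documents do not support a direction. If the product works as planned, deterioration could be commoner on placebo, and the bias would then tend to run against it.

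**What to change.** In 4.4, and consistently in 5.3.1 and 7.3, separate stopping study treatment from leaving the study. Leave the listed reasons for stopping treatment as they are; this point takes no view on them. State that children whose treatment is stopped continue the diary, questionnaires and adverse-event follow-up to week 10 unless consent to data collection is withdrawn, and that these data enter the ITT analysis. Reconcile the wording with 6.4 (unblinded children), 7.2.1 (SAE follow-up), 7.3 (pregnancy follow-up) and 10.2 (violations), including whether a child who takes no study treatment is a refuser who stays in follow-up or a violator who is withdrawn.

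The cost is protocol and consent-form wording and some extra remote follow-up. The diary is already online and the follow-up appointments are already remote.

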5. INTERVENTIONS AND STUDY DEVICE

5.1 INTERVENTION

5.1.1 Treatment allocation

5.1.1.1 Double-blind phase

For the double-blind treatment phase, patients will be randomised in 1:1 ratio using a computer-based randomisation tool (Sealed Envelope Ltd, UK) to:

Control Group: will receive placebo daily for 4 weeks

Interventional Group: will receive Enterosgel® daily for 4 weeks

Randomisation will be based on the minimisation method where treatment allocation will be stratified by study centre, sex and age group (15-18 years; 7-14 years and 3-6 years). Minimisation allocates subjects to the treatment group that best maintains balance in stratifying factors. It is effective even at small sample sizes and with multiple stratification variables [24].

5.1.1.2 Open-label phase

For the open-label treatment phase, all patients will receive Enterosgel® daily for 4 weeks in standard 225g tubes, which are identical to those available over-the-counter in the UK.

5.1.2.2 Description of study treatment

Although there has been extensive research on Enterosgel® in Eastern Europe, so far none of the conducted trials have included a placebo control arm. Any gel-like substances (for example gelatin or starch based) could potentially have effects in the gastrointestinal tract and their suitability for use as a placebo would require validation. However, since Enterosgel® is taken by diluting 1-1.5 tablespoons of the product in 200ml water, a water-based placebo is an alternative to a gel-like placebo. The recent RELIEVE IBS-D trial used water as the placebo and pre-diluted Enterosgel®, both were placed in identical 90g tubes [19], this approach was successful in achieving the first placebo trial of Enterosgel®.

The same approach will be used in this trial. The blinded Enterosgel® will be provided in a pre-diluted form in 90ml tubes containing Enterosgel® in potable water. The dose/weight of Enterosgel® in each tube will vary dependent on age of the child. The appropriate age-related dosed tubes will be provided to each participant. Diluting the Enterosgel® in water will not alter the structural or adsorption properties of Enterosgel® [25].

For the open-label phase, patients will be provided with the standard over-the-counter Enterosgel® in 225g tubes.

5.1.3 Placebo

Each placebo tube will contain 90ml of potable water.

5.1.4 Treatment dosage

5.1.4.1 Double-blind phase

Both the placebo and Enterosgel® will be provided in 90g tubes, each containing a single dose of treatment (age 7-18 years) or half a dose of treatment (age 3-6 years). Each Enterosgel® tube contains either 8, 12 or 18g of Enterosgel® (Bioline Products s.r.o, Czech Republic) pre-diluted in 65-80ml of potable water. Each placebo tube contains 90ml of potable water.

The age-related treatment dose per day is one dose in the morning 1 hour before or after a meal, and one dose in the evening 1 hour before or after a meal. The daily dose for week 1-2 will be 53% of the recommended age-related daily treatment dose for acute diarrhoea, the dose will increase at week 3-4 to 80% of the dose for acute diarrhoea.

Study-specific age-related dosage instructions for the double-blind treatment period are provided in **APPENDIX C: TREATMENT USE INSTRUCTIONS (DOUBLE-BLIND PHASE)**.

5.1.4.2 Open-label phase

For the open-label treatment phase, all patients will receive Enterosgel® in 225g tubes with the appropriate age-related measuring spoon (5g, 10g or 15g). The age-related dosage morning and evening and the stepwise dose increase at week 3-4 will align with the double-blind phase. Study-specific dosage instructions are provided in Error! Reference source not found.

5.1.5 Labelling, storage, supply and destruction

5.1.5.1 Blinded study treatment

Both the placebo and Enterosgel® dilution will be manufactured in accordance with good manufacturing practice (GMP) by Bioline Products s.r.o. and packed into identical 90g tubes.

In accordance with Annex I of the European Council Directive 93/42/EEC concerning Medical Devices, each study device will be marked with a label containing the text "EXCLUSIVELY FOR CLINICAL INVESTIGATION" and the following information:

- 1. Content: This tube contains blinded gel drink
- 2. Manufacturer: Bioline Products s.r.o, [name].
- 3. Distributor: Enteromed Ltd, UK
- 4. Study Sponsor: Enteromed Ltd, UK
- 5. Study reference: ENT08UK
- 6. Batch number: Please check crimped top of tube for number
- 7. Expiry date: Please check crimped top of tube for date
- 8. Instructions for use: Shake well immediately before use. Add the dose to the volume of room temperature water stated in study treatment instructions. Leave at least 2 hours before and after taking this treatment and taking any oral medications and 1 hour for eating meals.
- 9. Storage: +4C° to +30C°. Keep away from direct sunlight or heat.
- 10. Disposal: Contents can be safely disposed into the domestic waste. Packaging can be recycled.

The tubes will be stored at the same warehouse facility as the commercial medical device (Nivtar Distribution Limited, Duxford, UK) contracted by the Sponsor. The study supplies should be clearly separated from any other commercial supplies, and placebo and Enterosgel® will be separated into age groups and treatment arm by product name and barcode, so that they can be identified by the warehouse staff responsible for coordinating the study supplies. After each randomisation, the research team will email using a secure message encryption, a Supplies Request Form with the unique randomisation code and the participant's name, home address and phone number to a dedicated email address, which is only accessed by two unblinded study coordinators at the Sponsor's research team. A coordinator will check the randomisation code against a pre-generated randomisation code list provided by Sealed Envelope Ltd, stored in a locked safe only accessible by the unblinded coordinators. The coordinator will determine whether the code corresponds to placebo or Enterosgel® and will log onto the secure study online booking site to request for a shipment of a box (A or B) of tubes of the correct age group corresponding to the randomisation code, to the participant's home address to be used starting after the Baseline appointment. The online system will generate a unique code which can then be tracked through the system and will confirm dispatch. At the warehouse the patient delivery will be picked, scanned for barcode and a second checking process will re-scan before the delivery is packed and dispatched within 2 calendar days from receiving the request (next day for orders submitted before 2 pm). All parties should delete the request emails once confirmed received by the next party. However, paper copies of the forms should be kept at the sites, and a record of each delivery with barcode checks will be available from the warehouse reporting to allow for treatment accountability. Likewise, the unblinded study coordinators will keep a record on a secure password protected smartsheet containing no patient identifiable information.

The participants can dispose of the empty tubes at home in the domestic waste, as well as any unused tubes remaining at the end of the study. Should the participant run out of study treatment during the 4 weeks, they or their parent/guardian can request for more supplies by contacting the research nurse, who will submit a request to the Sponsor.

5.1.5.2 Open-label study treatment

After a participant has been entered into the open-label phase, the research team will email the participant's name, home address and phone number to a dedicated email address, as described above in section 5.1.5.1. The study coordinators receiving this information will then request a shipment of open-label treatment from the warehouse to the patient's home.

Each study device will be marked with a label containing the text "EXCLUSIVELY FOR CLINICAL INVESTIGATION" and the following information:

- 1. Content: This tube contains the treatment ENTEROSGEL®
- 2. Manufacturer: Bioline Products s.r.o, [name].
- 3. Distributor: Enteromed Ltd, UK
- 4. Study Sponsor: Enteromed Ltd, UK
- 5. Study reference: ENT08UK
- 6. Batch number: Please check crimped top of tube for number
- 7. Expiry date: Please check crimped top of tube for date
- Instructions for use: Shake well immediately before use. Add the correct dose using the measuring spoon to the volume of room temperature water stated in study treatment instructions. Leave at least 2 hours before and after taking this treatment and taking any oral medications and 1 hour for eating meals.
- 9. Storage: +4C° to +30C°. Keep away from direct sunlight or heat.
- 10. Disposal: Contents can be safely disposed into the domestic waste. Packaging can be recycled.

Participants can dispose of the empty tubes at home in domestic waste and keep any remaining unused Enterosgel®. Should the participant run out of study treatment during the 4 weeks, they can request for more supplies by contacting the research nurse, who will submit a request to the Sponsor.

5.3 CONCOMITANT TREATMENTS

5.3.1 Other FGID treatments

Participants will be allowed to continue to take antidepressant agents at a stable dose, provided that they had been taking a stable dose for at least 6 weeks before providing written informed consent.

Use of probiotic supplements, other intestinal adsorbents (activated charcoal, kaoline, diosmectite), slowrelease medications or strong opioids during the study will not be permitted and any participants who require slow-release medications, should be withdrawn from the trial. Participants will be advised not to make any changes to their diet while on the trial.

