	 Average number of stools per week <3 Previous use of Enterosgel® Use of antidepressant agents, unless used at a stable dose for at least 6 weeks Use of any probiotic supplements, other intestinal adsorbents, slow-release medications or strong opioids Participation in any research where treatment is provided in the last three months Pregnancy or not willing to use contraception for the duration of the study in females of childbearing potential defined as any female over 11 years of age and who has not undergone surgical sterilization (hysterectomy or bilateral conhorectomy) or is not postmenopausal
Study schedule:	Screening appointment in person/video conference (0 weeks) • Patient screening • Confirming eligibility • Informed consent • Demographic information • Medical history and concomitant medications • Provide information about the study Recruitment call – remote (0 weeks)
	 Informed consent Questionnaires (PedsQL 3.0 GIS module, KIDSCREEN-27) Initial observation period (weeks 1-2) Daily symptom diary (continue for 10 weeks) Baseline (remote): Start of double-blind phase (beginning of week 3) Review of changes in medical history and concomitant medications Instruction on use of study intervention Randomisation Double-blind study treatment received by post Follow-up call – remote (week 3)
	 Ensure participant continuing in the study and discuss any potential issues Adverse events Follow-up 1 appointment – remote (end of week 6) Questionnaires (PedsQL 3.0 GIS module, KIDSCREEN-27) Review of changes in medical history and concomitant medications Record Adverse Events Adequate relief question Check compliance and advise on any issues Open label study treatment received by post Follow-up 2 appointment – remote (end of week 10) Questionnaires (PedsQL 3.0 GIS module, KIDSCREEN-27) Review of changes in medical history and concomitant medications Record Adverse Events Adequate relief question Check if any arrangements for clinical follow-up as part of routine care

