3. STUDY DESIGN AND OUTCOME MEASURES

3.1 STUDY DESIGN

This is a UK two-centre, parallel arm, randomised, double-blind, placebo-controlled trial to evaluate the efficacy, tolerability and safety of a medical device, Enterosgel®, in the treatment of functional abdominal pain in children and young people. (**Figure 1**).

Children aged 3-18 years will be recruited over a 12-month period by review of NHS referrals to general paediatric and paediatric gastroenterology clinics at Alder Hey Children's NHS Foundation Trust, and Bristol Royal Hospital for Children and by review of children previously diagnosed with a FAPD. All children will be reviewed by an experienced paediatrician. A thorough clinical assessment including any appropriate investigations (e.g. gastro-intestinal endoscopy; abdominal ultrasound, faecal calprotectin) will be performed with careful attention to potential alarm features in children with chronic abdominal pain to ensure that other diagnoses are excluded [20]:

- Family history of inflammatory bowel disease, celiac disease, or peptic ulcer disease
- Persistent right upper or right lower quadrant pain
- Dysphagia
- Odynophagia
- Persistent vomiting
- Gastrointestinal blood loss
- Nocturnal diarrhoea
- Arthritis
- Perirectal disease
- Involuntary weight loss
- Deceleration of linear growth
- Delayed puberty
- Unexplained fever

Children will only be recruited once a diagnosis of an FAPD has been confirmed according to Rome IV criteria [21] and including the following syndromes:

- H2a. Functional Dyspepsia
- H2b. Irritable bowel syndrome
- H2c. Abdominal Migraine
- H2d. Functional Abdominal Pain Not Otherwise Specified

The study involves a screening clinic appointment (routine clinical care; week 0) and remote recruitment appointment, a two-week initial observation period (weeks 1-2), a follow-up remote appointment at Baseline week 3 to confirm eligibility and a call at week 4 to check compliance, and follow-up remote appointments at weeks 6 and 10. The daily on-line diary will be completed for 10 weeks (Wong-Baker FACES Pain Rating Scale) and questionnaires (PedsQL 3.0 GIS module, KIDSCREEN-27) at screening, 6 and 10 weeks. No further clinic visits or blood, stool or other samples are required for research purposes.

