5.3.2 Contraindications

The only listed contraindications for Enterosgel® are intestinal atony, use of slow-release medications and intolerance to Enterosgel® based on previous use. The study eligibility criteria will ensure that no participants with these contraindications will be enrolled into the trial.

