6.2 STUDY VISITS AND PROCEDURES

Participants will attend one screening study visit during a routine clinic visit (on site or remote) at the recruiting site followed by a remote Recruitment visit. Informed consent and assent (written or e-consent) will be obtained by the research nurse before any study procedures are conducted. Participants who pass the diagnostic criteria and consent to proceed will be entered into the study. Demographic and clinical data will be collected and questionnaires completed at the recruitment visit and participants entered into the observational phase. Further appointments/calls will be conducted by the research team; at baseline (week 3), week 4 and at the end of the double-blind phase (week 8) and end of the open label phase (week 10).

The schedule of appointments and procedures conducted at each visit are summarised in **Table 3** and described in more detail below. +/- 1 week is allowed around each follow-up appointment. **Table 4** summarises the schedule for completion of study diary and questionnaires. All remote appointments and follow-up calls, can be conducted either via telephone or video call, depending on the participant's preference. At the end of the study (week 10), children will continue under the care of their paediatrician usually including a routine follow-up clinic at week 12 (3 months from the initial screening visit).

Procedure	Screening appointment (Recruitment site/remote)	Recruitment appointment (remote)	Baseline appointment (remote) Week 3	Complian ce call Week 4	Follow-up 1 appointment (remote) 6 weeks	Follow-up 2 appointment (remote)10 weeks
	0 weeks					
Informed consent		Х				
Patient screening	Х					
Demographic information	x					
Review of medical history and concomitant medications	Х					
Pregnancy test where needed			x			
Instructions on completion of diary		x	x		X	
Confirming eligibility (based on patient diary data; review of medical notes; pregnancy test)			X			
Randomisation			Х			
Instructions on use of study treatment			X		X	

Table 3. Schedule of events and appointment procedures.

Review of changes in medical history or concomitant medications		Х		Х	Х
Adverse Events			х	Х	Х
Checking compliance to study procedures and advising on any issues			Х		
Adequate relief question				Х	Х

Table 4. Study diary and questionnaire completion schedule. "X" means that the item is completed once that week, except where otherwise specified.

Visit/study period	Week	Diary*	PedsQL-3.0-GIS	KIDSCREEN

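### Slow-release medicines require withdrawal, but the labels and family sheets shown give only a two-hour spacing rule, and after Baseline medication changes are reviewed only at weeks 6 and 10 (minor safety-conduct point)

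*Protocol*

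**What the plan says.** **The rule.** Section 5.3.1 bans four classes during the study: probiotics, other intestinal adsorbents, slow-release medicines and strong opioids. Only for slow-release medicines does it add a consequence: "any participants who require slow-release medications, should be withdrawn from the trial". Section 5.3.2 gives the reason. The listed contraindications are "intestinal atony, use of slow-release medications and intolerance to" the product on previous use, and that section relies on the eligibility criteria to keep such children out.

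**Entry.** Exclusion criterion 5 in section 4.2 covers slow-release medicines, and section 6.2.1.2 has the medication list checked at Baseline.

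**After Baseline.** The Table 3 row "Review of changes in medical history or concomitant medications" is marked at Baseline, follow-up 1 (week 6) and follow-up 2 (week 10), but not at the compliance call. Section 6.2.2 agrees. Section 6.2 adds that plus or minus "1 week is allowed around each follow-up appointment". For the compliance call, Table 3 marks adverse events and "Checking compliance to study procedures and advising on any issues". The trial summary's schedule describes the call as "Ensure participant continuing in the study and discuss any potential issues", plus adverse events.

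**Date of the call.** Section 3.1 has "a call at week 4 to check compliance", and the study design row of the trial summary, section 6.2 and Table 3 also say week 4. One line in the summary's schedule reads "Follow-up call – remote (week 3".

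**What families read.** Both tube labels (5.1.5.1 and 5.1.5.2) and the 7-14 year sheets in Appendices C and D give a two-hour separation from oral medicines. None of the four mentions slow-release products or asks the family to report a new medicine. The Appendix C sheet invites contact with the research nurse at any time; the Appendix D sheet does not.

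**Other records.** The diary (Appendix A) covers pain, doses taken and missed school. Outcome 11 in Table 1 covers only common analgesics, in weeks 2, 6 and 10. Violation item 9 in section 10.2 names three of the four classes banned in 5.3.1 and leaves out slow-release medicines.

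**The concern.** The protocol treats slow-release products differently from other oral medicines: the others need spacing (5.3.3), whereas these need withdrawal. The family-facing text shown applies one spacing rule to all of them. A parent whose child is prescribed a slow-release product in week 8 could read the sheet, space the doses, follow it exactly, and continue a combination that 5.3.1 says must stop.

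The withdrawal rule works only if someone on the study team learns of the new medicine. The scheduled question comes at the end of each phase. In the open-label phase, where every child takes the active product, that is about when dosing stops, so a withdrawal at that point protects little. What is at stake is the safe conduct of the study for individual children, not the treatment comparison.

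**Working it through.** No figure in the plan needs reproducing. The check compares the rule with the instructions and then measures the gaps between scheduled reviews.

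**Rule against instruction**

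| Source | Ordinary oral medicine | Slow-release medicine |
|---|---|---|
| 5.3.1, 5.3.2, 5.3.3 | two-hour spacing | contraindicated; withdraw |
| Labels; Appendix C and D sheets (7-14 years) | two-hour spacing | not distinguished, so two-hour spacing |

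The second column agrees and the third does not.

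**Gaps between scheduled medication reviews**

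Inputs: Baseline at the start of week 3 (day 0), follow-up 1 at the end of week 6 (day 28), follow-up 2 at the end of week 10 (day 56), and a window of 7 days either way. I assume that the window applies to the two follow-up appointments and that Baseline and the call keep their stated weeks. The narrative in 6.2 gives week 8 for the end of the double-blind phase. I use week 6, as in Table 3 and 6.2.2, because the phase lasts four weeks from week 3.

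- Baseline to follow-up 1: 28 − 0 = 28 days nominal; with the window, 21 to 35.
- Follow-up 1 to follow-up 2: 56 − 28 = 28 days nominal. With the window, the shortest is 49 − 35 = 14 and the longest 63 − 21 = 42.
- Planned dosing ends on day 56. In the 42-day case the review is on day 63, so 63 − 56 = 7 of those days come after planned dosing, leaving 42 − 7 = 35.

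**Effect of a medication question on the week 4 call**

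Let the call be on day c and follow-up 1 on day r. The longest gap is max(c, r − c). Week 4 is c = 7 to 14.

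- Nominal, r = 28: c = 7 gives max(7, 21) = 21; c = 14 gives max(14, 14) = 14. The longest gap falls from 28 to 14-21 days.
- With the window, r = 21 to 35: the best case is c = 10.5, r = 21, giving 10.5; the worst is c = 7, r = 35, giving 28. The range is 10.5-28 days, against 21-35 without the question.
- Open-label phase: no contact is scheduled between the two follow-up appointments, so the call changes nothing there. Only the sheet wording acts.

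These are intervals until a scheduled question is asked. They do not measure risk.

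**The case against.** The strongest reply is that the schedule is defensible. Entry is well controlled, a ban and a withdrawal rule exist, and medication changes are reviewed three times from Baseline on (Baseline, week 6 and week 10) across eight weeks of an over-the-counter product. In the double-blind phase about half the children take water. Other routes can bring a case to light: adverse events collected to week 10 (7.2.1), the issues raised on the call, the notified GP (4.3.2), unblinding requests when regular therapy is to change (6.4), and nurse instruction (6.2.1.6 and 6.2.2.1). All of this stands and keeps the point minor. None of it is a scheduled medication question between reviews, and none changes what the labels and sheets say.

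Four stronger readings are tempting and should not be drawn.

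- *Families are never told of the ban.* This cannot be shown. The information sheets and the sheets for other ages are not in the document, and nurses also give instructions. What can be shown is that the four texts in view do not make the distinction.
- *A child could dose for 42 days undetected.* That figure needs follow-up 1 a week early and follow-up 2 a week late, and its last 7 days follow planned dosing.
- *Violation item 9 lets a case escape.* The list is of examples, and the general definition in 10.2 covers safety. Section 5.3.1 already orders withdrawal, and a withdrawn child has not completed the study, so is outside the per-protocol population (8.3.2). The omission is editorial.
- *The call may be in week 3, so a question there gains little.* At c = 0 to 7 the longest nominal gap would be 21-28 days. That date appears in one line of the summary's schedule, against week 4 everywhere else, including the summary's own design row. It is a slip.

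**Conclusion.** The point holds as a minor safety-conduct improvement. The labels and the two sheets shown give one spacing rule where sections 5.3.1 and 5.3.2 require withdrawal, so the written instruction points away from the protocol's own safety rule. Scheduled medication reviews after Baseline are nominally 28 days apart, and the open-label review comes at about the end of dosing.

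The size in patients is unknown: the document gives no rate of new slow-release prescriptions and no estimate of harm. The conclusion assumes that the texts shown represent what families read about other medicines; if the information sheets already state the ban, only a wording mismatch remains. Sample size, error rate and the primary analysis are not affected.

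**What to change.** 1. On every age version of the Appendix C and D sheets, add that slow-release medicines must not be taken with the treatment and that the family must phone the research nurse before starting any new medicine. If the information sheets already say so, only align the wording. This also supplies the nurse-contact prompt missing from Appendix D. The line is the same in both arms, so blinding is unaffected.
2. In Table 3, add changes in concomitant medications to the existing week 4 compliance call.

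For consistency only, add slow-release medicines to violation item 9 in section 10.2 and correct the week 3 entry in the summary's schedule to week 4.

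The cost is one line on the sheets and one question on a call that is already planned. No visit, relabelling, diary item or analysis change is needed. The revised sheets and protocol text may need approval if they count as a substantial amendment (12.1), so the change is best bundled with another.
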